
Secondary
 
1. To compare detection rates of recurrent disease in blinded interpretations between the furosemide and non-furosemide ¹⁸F-rhPSMA-7.3 PET/CT scans, with patients serving as their own internal controls
 
Lesion detection rates on a patient and region basis will be recorded in addition to the ratio of
	Compare lesion detection and confidence between rhPSMA7.3 PET without and with furosemide

OBJECTIVES	ENDPOINTS

the lesion to background activity including blood pool, liver, spleen and parotid. Test retest of lesions and background measurements between the studies with furosemide and without furosemide will be performed.
 
2. To compare reader confidence in identifying prostate bed and other recurrent lesions on a 18F-rhPSMA-7.3 PET/CT with furosemide compared with 18F-rhPSMA-7.3 PET/CT without furosemide
 
The readers' (total two readers) confidence in the assessment of findings in the prostate bed and other locoregional and distant lesions will be rated using a five-point Likert scale with 1 being definitely benign and 5 being definitely malignant. The readers' confidence scores for both the PET/CT scans (with and without furosemide) will be compared. The readers will be blinded to the furosemide injection.
	
Tertiary/Exploratory	

2. Background

Prostate cancer is the most common cancer diagnosed in men in 2021 and accounted for 11% of all cancer-related deaths in men in the United States. Early diagnosis is desirable so that definite treatment with curative intent can be offered. RP is a suitable definitive therapy offered to patients with early-stage disease. Complete tumor resection during RP with or without pelvic lymph node dissection results in serum PSA level decline below detectable limits. PSA can then subsequently be used as a sensitive and specific tumor marker in the early detection of disease recurrence. The American Urological Association and European Association of Urology guidelines define biochemical recurrence after RP as an initial PSA value of 0.2 ng/mL or greater, measured 6 weeks after surgery to allow appropriate washout of any residual PSA. This result is confirmed by a subsequent PSA value of 0.2 ng/mL or greater to rule out a laboratory error[1, 2]. The risk of biochemical recurrence is associated with the baseline risk categorization of the disease, with patients in higher-risk groupings having

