We hypothesize that the administration of intravenous furosemide at the time of radiotracer injection will reduce the activity of ¹⁸F-rhPSMA-7.3 in the urinary bladder and facilitates the identification of prostate bed recurrence in men with rising serum PSA post-prostatectomy. We also hypothesize that reduced urinary activity of ¹⁸F-rhPSMA-7.3 will improve readers' confidence in assessing prostate bed recurrence of prostate cancer. An improved lesion detection will influence management decisions.

To test these hypotheses with the highest scientific rigor, we propose a study including men with BCR post-prostatectomy. Each patient will undergo two sets of ¹⁸F-rhPSMA-7.3 PET/CT scans, one with and the other without furosemide, and the level of urinary bladder activity, the detection rate of prostate bed recurrence and other lesions, will be compared between the two scans. In this manner, each patient will serve as their own control. We expect that the results from this study may generate sufficient evidence that may affect the workflow of ¹⁸F-rhPSMA-7.3 PET/CT imaging of BCR of prostate cancer, especially after FDA approval for use in routine clinical care.

2.4 3.2 Clinical Experience

Our preliminary data support a key scientific premise that the intravenous administration of furosemide at the time of radiotracer injection leads to lower radiotracer concentration in the urinary bladder. This finding is supported by published studies in the literature showing that intravenous administration of furosemide at the time of ⁶⁸Ga-PSMA-11 administration causes a reduction in

bladder activity, improves detection of local prostate bed recurrence, and improves reader confidence. Study Intervention/Investigational Agent

2.5 4.1 Description

IV injection of 8 mCi (296 MBq) \pm 20% of rhPSMA-7.3 (18F) diluted up to 10 mL will be used for each of the two PET scans. This dose is based on dosimetry data obtained from published phase I study data [21], and the dose utilized in the approval phase III trial that was recently concluded [NCT04186845]. The study will be performed under IND #162587 held by [name].

2.6 4.2 Drug/Device Handling

- Radiotracer handling and administration: Each individual dose of radiotracer will be specifically ordered and delivered on the day of the study for the research subject and administered by authorized personnel per standard radiotracer administration protocol of the institution and division.

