We will image 20 patients with biochemical recurrence of prostate cancer post-prostatectomy for this study. Based on prior observation, we assume an SUV mean of 9.2 (SD=11.1) in those receiving 20mg furosemide IV at the time of radiotracer injection, and an SUV mean of 2.6 (SD=1.0) in those not receiving furosemide (White Paper Prepared for Syncona: Evaluation of 18F-rhPSMA7, Unpublished). Assuming a correlation between paired measurements of 0.5 which results in a standard deviation of change in SUV mean of approximately 10, we have 80% power to detect that change in SUV mean (9.2 vs. 2.6) with 20 patients, assuming a Type I error of 0.05, using a paired t-test. The sample size was calculated using PASS 2020 v20.0.3.

Populations for analyses

Efficacy set: All patients administered both 20mg furosemide IV at the time of radiotracer injection and without furosemide.

Safety set: All patients receive a dose of the radiotracer with each study.

Statistical analyses:

General Approach

Continuous variables will be summarized using mean, median, interquartile range, standard deviation, and min/max. Categorical variables will be summarized using frequencies and percentages. All tests will be two-sided with an alpha level of 0.05, unless otherwise noted. Testing assumptions will be

assessed and verified. Statistical analysis will be conducted using SAS 9.4 (SAS Institute Inc., Cary, NC).

Analysis of the Primary Efficacy Endpoint

Change in bladder SUV mean: The primary endpoint is change in bladder activity, as measured by bladder SUV mean, between administration of 20mg furosemide IV at the time of radiotracer injection and without furosemide. Change in bladder SUV mean will be assessed using a paired t-test, or using a non-parametric equivalent such as a Wilcoxon signed rank test. Descriptively, change in bladder SUV mean will be reported for those administered 20mg furosemide IV at the time of radiotracer injection first (Group A), and those administered 20mg furosemide IV at the time of radiotracer injection second (Group B).

Analysis of the Secondary Endpoints:

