Bladder and renal activity: Change in bladder and renal activity, as measured by bladder SUV max, bladder volume, and renal SUV mean/max, between administration of 20mg furosemide IV at the time of radiotracer injection and without furosemide will be assessed using paired t-tests, or using non-parametric equivalents such as a Wilcoxon signed rank tests. Descriptively, bladder and renal activity will be reported for those administered 20mg furosemide IV at the time of radiotracer injection first (Group A), and those administered 20mg furosemide IV at the time of radiotracer injection second (Group B).

Recurrent disease rate: Recurrent disease is defined as presence of unequivocal soft tissue radiotracer uptake that is characteristic of malignancy in the prostate bed and/or surrounding soft tissues and within pelvic lymph nodes. Recurrent disease rates will be compared (furosemide vs. non-furosemide 18F-rhPSMA-7.3 PET scans using McNemar's tests. Rates will be reported, along with 95% exact confidence intervals using the Clopper-Pearson method. Descriptively, recurrent disease rate will be reported for those administered 20mg furosemide IV at the time of radiotracer injection first (Group A), and those administered 20mg furosemide IV at the time of radiotracer injection second (Group B).

Confidence score: The readers' confidence in identifying prostate bed, pelvic and retroperitoneal nodal disease and other recurrence on 18F-rhPSMA-7.3 PET/CT with furosemide compared with the 18F-rhPSMA-7.3 PET/CT without furosemide will be scored using a 5-point Likert scale. This analysis will be descriptive, with summary statistics reported with and without furosemide.

Safety Analyses: Not applicable.

Baseline Descriptive Statistics

Patient characteristics will be summarized descriptively, using mean, median, interquartile range, min/max, and standard deviation for continuous variables, and using frequencies and percentages for categorical variables.

Interim Analysis: N/A

16.2 Data/specimens:

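### The recurrent-disease definition in Section 11.1 pools the prostate bed with pelvic nodes, omits bone and extrapelvic sites, and leaves the promised prostate-bed comparison unspecified

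*Combined protocol and SAP*

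**What the plan says.** **Hypothesis.** Section 3.1 Study Rationale, repeated under Scientific Rationale for Study Design, expects that furosemide "facilitates the identification of prostate bed recurrence in men with rising serum PSA post-prostatectomy". The same text commits to comparing detection between the two scans, both in the prostate bed and for other lesions.

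**Objective.** Secondary Objective 1 concerns detection of recurrent disease, with no restriction by site. The objectives table adds: "Lesion detection rates on a patient and region basis will be recorded".

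**Reading.** Under Overall Design, the readers identify and rate suspicious lesions for both loco-regional and distant disease. The confidence score in Section 11.1 covers "prostate bed, pelvic and retroperitoneal nodal disease and other recurrence", but is descriptive only.

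**Analysis.** Section 11.1, Recurrent disease rate, gives one definition: unequivocal soft-tissue uptake characteristic of malignancy "in the prostate bed and/or surrounding soft tissues and within pelvic lymph nodes". Rates with and without furosemide are compared by McNemar's tests, with Clopper-Pearson intervals for each rate. No region is named for testing, no bed-only comparison is listed, and the text does not say whether McNemar is exact or asymptotic.

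**The concern.** Furosemide is expected to help where bladder activity obscures disease, which is the prostate bed. The one detection endpoint that is tested mixes the bed with pelvic nodes. Eligibility does not exclude node-positive patients and allows earlier salvage therapy, so some may have nodal uptake on both scans. Such a patient is concordant whatever the bed shows. Conversely, a change in nodes alone would count as a detection gain.

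A second, independent mismatch is scope. Disease confined to bone or retroperitoneal nodes is scored by the readers but classed as no recurrent disease, so the reported rate is not the rate that Secondary Objective 1 names.

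Third, the connectives allow two codings of the endpoint, and they treat the same patient differently. At stake are the meaning of the reported detection rate and whether the bed comparison is prespecified or chosen after the data are seen.

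**Working it through.** **Plan's own figure.** Section 11.1 states no power for the detection rate. Its only power figure is for bladder SUVmean: 80% with 20 patients. A two-sided paired t-test (noncentral t) with difference 9.2 − 2.6 = 6.6 and SD of change 10 gives 79.9%, which reproduces. The unrounded SD, √(11.1² + 1.0² − 2×0.5×11.1×1.0) = 10.64, gives 74.9%. Neither value bears on detection.

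**How patient patterns are classified**

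| Pattern | Bed or nodes | Bed and nodes | Bed only | Any site |
|---|---|---|---|---|
| Bed seen only with furosemide, no other disease | discordant | concordant negative | discordant | discordant |
| Bed seen only with furosemide, nodes positive on both | concordant positive | discordant | discordant | concordant positive |
| Nodes seen only with furosemide, no other disease | discordant | concordant negative | concordant negative | discordant |
| Bone or retroperitoneal disease only, on both | concordant negative | concordant negative | concordant negative | concordant positive |

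The first two columns are the two readings of the definition. They disagree on the first three rows. Only the bed-only column isolates the hypothesised effect, and only the any-site column classifies the last row as recurrent disease.

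**Inputs for size**
- n = 20 ("We will image 20 patients with biochemical recurrence of prostate cancer post-prostatectomy for this study").
- Two-sided alpha 0.05 ("All tests will be two-sided with an alpha level of 0.05, unless otherwise noted").
- Bed gain g = 25.5% − 17.3% = 8.2 points. This is the only bed effect in the documents (Background). It comes from another tracer and compares different patients.
- q = share of the bed gain falling in patients node-positive on both scans. The documents do not give it; a range is assumed.

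**Dilution (bed-or-nodes reading).** Expected patients gained = 20 × g × (1 − q):
- q = 0: 20 × 0.082 = 1.64
- q = 0.2: 1.64 × 0.8 = 1.31
- q = 0.5: 1.64 × 0.5 = 0.82

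Under the bed-and-nodes reading, a bed gain registers only in patients with positive nodes. From that group the figures are 1.64 × 0.2 = 0.33 and 1.64 × 0.5 = 0.82.

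**Smallest significant result, all discordance one way**
- Exact, p = 2 × 0.5^k: k = 5 gives 0.0625 and k = 6 gives 0.031, so six pairs are needed.
- Uncorrected chi-square, statistic = k: k = 3 gives p = 0.083 and k = 4 gives 0.046, so four pairs are needed.

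**Power with no reverse discordance.** P(Bin(20, g(1 − q)) ≥ 6) for exact, ≥ 4 for uncorrected:

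| q | Gain seen | Exact | Uncorrected |
|---|---|---|---|
| 0 (same as bed only) | 8.2 points | 0.43% | 7.6% |
| 0.2 | 6.6 points | 0.14% | 3.8% |
| 0.5 | 4.1 points | 0.01% | 0.8% |

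Allowing 2% or 5% reverse discordance, bed-only power is 0.9% or 1.9% (exact) and 9.9% or 11.1% (uncorrected). With no reverse discordance, 80% power at n = 20 needs a bed gain of about 37 points (exact) or 26 points (uncorrected). At 8.2 points, the exact test needs about 95 patients.

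**If the effect were large.** With an assumed 40-point bed gain, exact power on the pooled endpoint is 87% at q = 0, 66% at q = 0.2 and 34% at q = 0.4.

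**The case against.** - **Regional tests may be intended.** Section 11.1 speaks of rates and tests in the plural, detection is to be recorded by region, and the rationale promises a bed comparison. This shows that the data will exist and that the intention is there. But the plural follows a single definition and names no region, so a regional comparison would still have to be chosen later.
- **A reader might infer that the McNemar test cannot show a bed gain.** The documents do not support that. Under the bed-or-nodes reading, a bed lesion gained in a node-negative patient still changes the result. Pooling dilutes and blurs attribution; it does not abolish the effect.
- **A reader might also infer that leaving out bone and extrapelvic sites hides a bed gain.** It does not. Adding those sites to a patient-level composite makes more patients concordant and masks the bed further. The omission is a separate fault, against the objective.
- **Sample size is the main limit.** This stands. At the cited gain, a bed-only test fails to reach significance more than 92% of the time even by the uncorrected method with no reverse discordance. At that gain, a null result should not be blamed mainly on how the endpoint is built.
- **The effect size is weak evidence.** This stands too. The cited study compared hydration plus furosemide with neither, whereas here both scans include oral hydration.
- **Secondary Objective 1 names recurrent disease, not the bed.** This is a fair reason not to move the only detection test to the bed.

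**Conclusion.** The mismatch is real, and following Section 11.1 as written would produce it. The section omits the bed comparison that the rationale promises, uses a definition narrower than both the objective and the read, and words it so that two codings are possible.

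The size of the dilution rests on two assumptions: that the 8.2-point gain transfers to this tracer and design, and that 20% to 50% of it falls in patients node-positive on both scans. On those terms the pooled endpoint registers 1.31 to 0.82 patients instead of 1.64. The classification faults need no such assumption. Correcting the endpoint changes what is estimated. It does not make 20 patients enough for a detection test at this effect size.

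**What to change.** In Section 11.1, Recurrent disease rate:

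1. Define patient-level recurrent disease as unequivocal uptake characteristic of malignancy at any site the readers record: bed or surrounding soft tissue, pelvic nodes, extrapelvic nodes, bone, or other. Join the sites by 'or' and drop the soft-tissue restriction.
2. Keep McNemar on that rate, to match Secondary Objective 1, and state whether the test is exact.
3. Prespecify prostate-bed detection as a separate per-patient comparison. Report the paired difference with a 95% confidence interval and both discordant counts. This is needed all the more once the composite is widened, because any-site disease on both scans masks the bed further.
4. Report the other regions descriptively.
5. State that the bed comparison is estimation, and give the power figures above as the reason.

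The cost is SAP wording, one additional secondary estimate and slightly more analysis work. Region-level findings are already to be recorded, so no new reads or patients are needed.

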APPENDIX C Abbreviations and definition of terms47

1. Study Summary

1.3 1.1 Synopsys

Title:	Strategy to Reduce Bladder Activity with rhPSMA 7.3: Comparison of 18F-rhPSMA 7.3 PET/CT with and without Furosemide in Biochemical Recurrence of Prostate Cancer
Study Description:	This research study is a single arm, Phase II study, designed to evaluate if administering furosemide at the time of 18F-rhPSMA 7.3 administration for PET/CT evaluation of prostate cancer patients with biochemical recurrence, significantly reduces bladder activity compared with the same patient scanned without furosemide as internal control
Objectives:	Primary Objective: To determine if administering 20 mg furosemide IV at the time of radiotracer injection significantly reduces bladder activity compared with the same patient scanned without furosemide as internal control Secondary Objectives: 
• To compare detection rates of recurrent disease in blinded interpretations between the furosemide and non-furosemide 18F-rhPSMA-7.3 PET/CT scans, with patients serving as their own internal controls• To compare reader confidence in identifying prostate bed and other recurrent lesions on a 18F-rhPSMA-7.3 PET/CT with furosemide compared with 18F-rhPSMA-7.3 PET/CT without furosemide
Endpoints:	Primary Endpoint: Determine the difference in the urinary bladder activity on ¹⁸ F-rhPSMA-7.3 PET/CT with furosemide compared with ¹⁸ F-rhPSMA-7.3 PET/CT without furosemide in biochemical recurrence of prostate cancer post radical prostatectomy (Specific Aim 1). Secondary Endpoints: Compare lesion detection and confidence between rhPSMA7.3 PET without and with furosemide.
Study Population:	The patient population consists of 20 subjects ≥ 18 years of age with biochemical recurrence of prostate cancer after radical prostatectomy.
Phase:	Phase II
Description of Sites/Facilities Enrolling Participants:	
• Emory University Hospital, Clifton Campus• Emory University Hospital Midtown• Emory University Hospital Johns Creek• Emory University Hospital St. Joseph's

[figure not shown]

Protocol Title: Strategy to Reduce Bladder Activity with rhPSMA 7.3: Comparison of 18F-rhPSMA 7.3 PET/CT with and without Furosemide in Biochemical Recurrence of Prostate Cancer

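### Reader confidence is to be compared between the two scans, but section 11.1 plans only separate summaries by condition, with no paired summary of the change

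*Combined protocol and SAP*

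**What the plan says.** The Synopsis and the objectives table in section 2 state secondary objective 2 as "To compare reader confidence in identifying prostate bed and other recurrent lesions" on the scan with furosemide against the scan without. The objectives table adds that the readers' "confidence scores for both the PET/CT scans (with and without furosemide) will be compared". It gives the matching endpoint as "Compare lesion detection and confidence between rhPSMA7.3 PET without and with furosemide".

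Section 3.1 (Study Rationale) hypothesises that lower urinary activity will improve the readers' "confidence in assessing prostate bed recurrence of prostate cancer". The two passages headed Scientific Rationale for Study Design repeat this. Of the two scans per man, section 3.1 says: "In this manner, each patient will serve as their own control".

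The Confidence score paragraph in section 11.1 names a five-point Likert scale and then says: "This analysis will be descriptive, with summary statistics reported with and without furosemide". It mentions no within-patient change, interval, paired table or test. The General Approach paragraph adds only one-variable summaries.

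In the same section, changes in bladder SUVmax, bladder volume and renal SUV "will be assessed using paired t-tests, or using non-parametric equivalents such as a Wilcoxon signed rank tests", and recurrent disease rates are compared by McNemar's test.

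**The concern.** The objectives promise a comparison within men, and the design is built to supply one. Confidence is the one named secondary objective for which section 11.1 sets out no paired summary. Two columns of summary statistics do not show whether a small shift came from a few men who all moved the same way or from many who moved in both directions. The trial could therefore report a higher average with furosemide and have no planned statement of how certain that difference is, although it would hold the data to make one.

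**Working it through.** **The plan's own figure.** The documents give no SD, correlation, effect or power for the confidence score. The only power figure, 80% for bladder SUVmean, belongs to the primary endpoint. With a change of 9.2 - 2.6 = 6.6, SD of change 10, n = 20 and a two-sided paired t-test at 0.05, it comes out at 79.9%. It does not bear on this point.

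**What summaries by condition retain.** For n men with both scores, mean(with) - mean(without) = mean(with - without), so the mean change can be recovered. Its standard error is SD(d)/sqrt(n), where d is the within-man change and

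SD(d)^2 = SD(with)^2 + SD(without)^2 - 2 r SD(with) SD(without).

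The correlation r is not in the summaries, so neither SD(d) nor the interval is. Nor are the median of d or the counts of men who improved or worsened.

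**Constructed example, n = 20 (section 11.1), one score per man per scan.**

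- Without furosemide: ten scores of 3 and ten of 4. Mean 3.50, SD sqrt(5/19) = 0.51.
- With furosemide: five scores of 3 and fifteen of 4. Mean 3.75, SD sqrt(3.75/19) = 0.44.

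If k men worsen by one point, these summaries force k + 5 to improve, with k from 0 to 5. The mean change is always 5/20 = 0.25. The sum of squared deviations of d is (2k + 5) - 20 x 0.25^2 = 2k + 3.75. The 95% CI is 0.25 ± 2.093 x SD(d)/sqrt(20), with 2.093 the t quantile on 19 df.

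| Improved / worsened | SD(d) | Implied r | 95% CI for mean change |
|---|---|---|---|
| 5 / 0 | sqrt(3.75/19) = 0.444 | 0.58 | 0.04 to 0.46 |
| 6 / 1 | sqrt(5.75/19) = 0.550 | 0.35 | -0.01 to 0.51 |
| 7 / 2 | sqrt(7.75/19) = 0.639 | 0.12 | -0.05 to 0.55 |
| 10 / 5 | sqrt(13.75/19) = 0.851 | -0.58 | -0.15 to 0.65 |

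The last row is the extreme and needs a negative correlation, which is unlikely within the same man. The first three rows all have positive correlation, and they already fall on both sides of zero.

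**What the scale measures.** The objectives table and the Overall Design text anchor the score at 1 for definitely benign and 5 for definitely malignant. Suppose ten men move from 3 to 5 and ten from 3 to 1. Every reading has become more certain, yet the mean signed change is (10 x 2 - 10 x 2)/20 = 0. With certainty taken as the distance from 3, each man changes by +2. A paired change in the raw rating would therefore measure suspicion. The table above carries over to the certainty score, because ratings of 3 and 4 become 0 and 1 and every change stays the same.

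**Whether a pair exists.** The Overall Design text has readers rate the suspicious lesions that they identify on each scan, blinded to the other scan. A region suspicious on one scan only may then have a score on one side only.

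**Precision to expect from a paired summary (illustration only).** Assume a score SD of 1 in each condition. The half-width of the 95% CI is 2.093 x sqrt(2(1 - r)/20), which gives 0.55, 0.47, 0.36 and 0.30 for r = 0.3, 0.5, 0.7 and 0.8. These scale in proportion to the SD, which on a 0-to-2 certainty score would probably be smaller.

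**The case against.** The strongest defence is that this is a disclosed choice. Section 11.1 calls the trial an early phase study and gives reduced bladder activity as its objective. The 20 men were sized for bladder SUVmean alone. Promising a comparison does not commit the plan to a test, and the sentence on confidence does not forbid a paired table. The hypothesis of improvement stands in the rationale and not in the objective. All of this is sound, and it means that no formal test is owed. It does not explain why the descriptive summary should ignore the pairing, because a within-man change with an interval is also descriptive.

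Three stronger readings are tempting, and the documents do not support them.

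- A reader might infer that the plan leaves no estimate of the change at all. With complete pairs, the difference of the two means is that estimate. The efficacy set requires both scans, and a man who misses the second is replaced. Pairs may still be incomplete for a region or lesion.
- A reader might infer that the trial cannot say whether confidence improved. It can report a difference in means. What is missing is a planned statement of its uncertainty and of how many men moved each way.
- A reader might infer that the planned interval is 1.4 to 2.2 times too wide. With SD 1, the standard error treating the scans as two separate groups is sqrt(2/20) = 0.316. Paired, it is sqrt(2(1 - r)/20) = 0.224, 0.173 and 0.141 for r = 0.5, 0.7 and 0.8. The arithmetic is right, but the correlations are assumed and section 11.1 plans no unpaired interval. The ratio describes an analysis that nobody has proposed.

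**Conclusion.** The mismatch is real and modest. The objectives promise a comparison of confidence, and section 11.1 delivers two separate descriptions without the within-patient precision, the median change or the counts improved and worsened. The example shows that this can matter: with the same reported summaries, the interval for a change of 0.25 may exclude or include zero. That is a constructed case with one score per man per scan and a t-based interval, which is approximate on so coarse a scale. It is not a forecast for this trial. That the pairing is lost follows from the design, whatever score is used. A paired summary is meaningful only once the score measures certainty and exists on both scans. The primary endpoint and the other secondary analyses are unaffected. This is a worthwhile, cheap improvement and not a fault in the trial's main conclusion.

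**What to change.** Keep the planned summaries by condition and add the following to the Confidence score paragraph of section 11.1.

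1. **Unit.** From the independent blinded reads, each reader records one rating per region on each scan for every man, prostate bed first, including regions read as negative.
2. **Score.** Convert the 1-to-5 rating to a certainty score, for example its distance from the midpoint 3, so that a change reflects confidence and not suspicion.
3. **Estimate.** For each man and region, take the with-minus-without change for each reader and averaged over the two readers. Report the mean and median change, with a 95% CI for the mean.
4. **Counts.** For each reader and region, give a paired shift table with the numbers improved, unchanged and worsened.
5. **Testing.** A signed-rank p-value is optional. If given, label it nominal.

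The cost is a short change to the analysis text, slightly more analysis and possibly a case report form field for negative regions. It needs no extra patients, scans or readers. The rating rule should be settled before reading starts, because ratings of negative regions that were not recorded at the blinded read would be hard to obtain later.
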